Figure 2: The ATP production rate assay demonstrates increased % glycolysis-derived ATP production in PBMC from T2D children. Oxygen consumption rate (OCR) (A) and Proton Efflux Rate (PER) (B) are plotted over time in PBMCs from lean, obese (OB) and type 2 diabetic (T2D) children. Injections of Oligomycin (oligo) and Antimycin A (AMA) and Rotenone (ROT) are indicated. (C) Glycolytic ATP production rate (glycoATP) and mitochondrial ATP production rate (mitoATP) are calculated from OCR and PER. (D) % glycolysis and % OXPHOS-derived ATP production are calculated. * $p=0.032$

Methods: Freshly isolated PBMC from lean ($n=8$), obese (OB; $n=11$), and treatment-naive type 2 diabetic (T2D; $n=2$) children were plated at 2.5×10^6 cells/well in RPMI 1640 with 1mM HEPES, 2mM glutamine, 1mM pyruvate and 11mM glucose on poly-D-lysine coated XF96 plates. Plates were centrifuged at 100xg with no brake to adhere cells to well bottoms. After a 30 min incubation in a 37°C non-CO₂ incubator, cells were assayed in a Seahorse XF96.

note regarding this data: 1) these data are from PBMC, a mixed population of cells including monocytes and lymphocytes of various subtypes rather than purified CD4⁺ T cells as proposed in this study; 2) the obese subjects have not been classified as metabolically healthy or unhealthy; 3) the age of the T2D subjects is greater (16.5±0.1 years; mean±SD) than the other groups (lean: 6.8±1.1 years; obese: 7.9±1.4 years). In the studies proposed herein, we will match groups on age and subgroup obese subjects as metabolically healthy and unhealthy based on insulin sensitivity. Further, after measuring high sensitivity CRP (hsCRP), we will compare subjects with hsCRP values in the top quartile to the other groups to determine whether the % glycolysis is higher in CD4⁺T cells from those obese subjects with inflammation.

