OXPHOS/Glycolysis (OCR/ECAR; **Figure 3C**). These data demonstrate our ability to measure mTOR activation in small numbers of immune cells from children.

Hypothesis, Specific Aims, and Objectives

In this study, we hypothesize that compared to lean children, circulating CD4⁺T cells from obese children with elevated biomarkers of inflammation will have fewer T_{regs} and will exhibit increased mTOR-driven glycolysis. Metformin treatment will increase T_{regs} and shift the metabolic phenotypes of CD4⁺T cells towards AMPK-driven OXPHOS. We will test these hypotheses by executing the following Specific Aim:

Specific Aim 1. Compare the immune and metabolic phenotypes of circulating CD4⁺T cells between lean children and overweight/obese children.

Hypothesis: circulating CD4⁺T cells from obese children with elevated biomarkers of inflammation will have fewer T_{regs} and will exhibit increased mTOR activation and % glycolysis-derived ATP production as compared to CD4⁺T cells from lean children.

Specific Aim 2. Compare the immune and metabolic phenotypes of circulating CD4⁺T cells between T2D children before and after metformin.

Hypothesis: In obese T2D patients, metformin treatment will increase circulating T_{regs}, as well as AMPK activation and % OXPHOS-derived ATP production in CD4⁺ T cells.

Study Design and Procedures

This study consists of:

1. An observational cross sectional immune and metabolic analysis of several groups of children including lean, overweight/obese, and T2D.
2. A prospective immune and metabolic analysis of newly diagnosed children with T2D or insulin resistance who will be or were recently prescribed metformin as part of their clinical care.

Children with T2D or insulin resistance who will be or were recently prescribed metformin, will be asked to complete two study visits. If completed, the second visit will occur 6 months (+/- 2 weeks) after beginning metformin as part of their clinical care. All other children, will be asked to complete only the first visit.

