At the initial study visit eligible participants will be met by study staff at the designated study location. Participants will arrive after not taking seasonal allergy medication in the previous 72 hours and an overnight fast of no food or liquid after 12 am, except for water and medications the day of the visit. The study visit may include collection of anthropometric measurements, tanner stage assessment, physical activity questionnaire, depression scale, body composition by bioelectrical impedance, blood, stool, and urine collection. Attempts to repeat anthropometric measurements, and body composition by bioelectrical impedance, will occur if a reading is not given the first time or if the child is unable to comply during the first measurement. For optional sample collection (i.e., urine and stool), the parent and participant will not have to stay at the research location for the entire visit in order for the samples to be obtained. Instructions will be given to the parents for collection of samples if the parent and child decide not to remain at the research location for the entire visit.

If a procedure(s) (see below) is not successfully completed, the parent and, if warranted, the participant may be asked to return to the study site for an additional visit to re-attempt the procedure. The decision to ask the parent/participant, to return for another attempt will be made by the principal investigator. When a decision is made to re-attempt the procedure, study staff will contact the parent and explain what procedure they would like to re-attempt and if the parent is willing, schedule the visit. If a blood draw will be re-attempted, the parent will be re-advised that if the parent wishes their child to complete the procedure, the child will need to not have taken seasonal allergy medication in the previous 72 hours and be fasting including no food or liquid after 12 am, except for water and medications the day of the visit. The study visit will be conducted in the same manner as the initial visit, with only the desired procedure(s) being re-attempted.

Title: Immunometabolism in Pediatric Obesity

PI: [name].

The collection of urine and stool samples is optional, and these samples may not be collected if the subject or parent does not want the sample(s) to be used for future research.

Study Procedures to be conducted at each visit:

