to complete the procedure(s). At the first, second, or reattempt visits, participants/parents may be given up to \$20 in ACRI merchandise and/or child-friendly stickers. Food and drinks may be provided during study visits following the fasting blood draw.

Study Population

110 children ages 5-17 years old will be recruited with the goal that approximately 80 subjects stratified across the following groups will complete the study: i) healthy lean (approximately n=20); ii) overweight/obese (approximately n=40, with the anticipation that approximately 20 of these children will be insulin resistant); iii) overweight/obese with T2D and prescribed Metformin (approximately n=20). Every attempt will be made to ensure that the desired number for each group is achieved and groups are balanced with respect to age, sex and ethnicity.

Inclusion Criteria:

- Age 5-17 years, inclusive
- Either healthy lean ($BMI \geq 5^{\text{th}}$ percentile and $< 85^{\text{th}}$ percentile for age/sex) or overweight ($BMI \geq 85^{\text{th}}$ percentile and $< 95^{\text{th}}$) or obese ($BMI \geq 95^{\text{th}}$ percentile for age/sex)
- For those with $BMI \geq 85^{\text{th}}$ percentile for age/sex, parental verbal confirmation that the child had a history of $BMI \geq 85^{\text{th}}$ percentile for age/sex for at least six months prior to study enrollment

OR

- Age 5 years - 17 years 5 months, inclusive
- Either overweight or obese ($BMI \geq 85^{\text{th}}$ percentile for age/sex)
- Parental verbal confirmation that the child had a history of $BMI \geq 85^{\text{th}}$ percentile for age/sex for at least six months prior to study enrollment
- Diagnosed with type 2 diabetes mellitus or insulin resistance
- Prescribed metformin (either not yet taking or began taking within 3 weeks of enrollment)

Exclusion criteria:

- Having an infection (viral, respiratory, gastrointestinal) in the previous 4 weeks
- Genetic or physical conditions impacting mobility over past year as determined by the PI
- Having known chronic illnesses/disorders that may independently affect study outcome measures: type 1 diabetes mellitus, neurologic (e.g. epilepsy), developmental (developmental delay, autism spectrum disorder), endocrine (thyroid, Cushing's), hepatic, autoimmune, cardiac and renal disorders. Also, chronic lung disorders except well controlled asthma that does not require permanent use of inhaled/oral steroids

Title: Immunometabolism in Pediatric Obesity

PI: [name].

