- Taking any of the following medications that can affect study outcome: antipsychotics, thyroid hormone replacement therapy, inhaled/oral steroids, insulin, anabolic drugs (growth hormone replacement therapy and oxandrolone) and stimulants
- Taking metformin prescribed as part of their clinical care for longer than 3 weeks at the time of enrollment (may begin metformin therapy prescribed as part of their clinical care while enrolled in the study)
- BMI<5th percentile for age/sex (classified as underweight based on CDC growth charts)
- Subjects determined ineligible by the PI or delegated staff.

Recruitment:

Study investigators, research staff, or any qualified personnel will conduct recruitment of study participants using IRB approved advertisements and methods.

We will recruit some subjects who agreed to be contacted for future research from an ongoing human research study, Bioenergetics and Metabolism in Pediatric Populations (BMPP; UAMS IRB #206164; [name] and [name], Co-PIs). In the BMPP study, we have enrolled 55 children in a period of 1 year and thus, we do not anticipate difficulty meeting this recruitment goal as the recruitment criteria are relaxed, with a wider age range, for the proposed study.

Advertisements may be distributed in the form of postcards or flyers via direct mail, at information booths or events, or to various locations for posting or distributing, including pediatricians' offices, health fairs, daycare centers, schools/universities, recreational centers, grocery stores, supermarkets, child retail stores, websites (ACH, ACRI, ACNC, UAMS, and others as applicable), and churches. Also, print or digital ads may appear in newspapers, magazines, social media, newsletters, and circulars. On-hold phone messages, BoomText messages, screensavers, and radio/television advertisements may be used. In addition, research staff may contact parents who expressed an interest in our studies or who previously agreed to be contacted regarding future studies. Research staff may also contact parents who have signed up for the AC research registry. The research staff will educate the parents and children about the study and if interested determine potential eligibility. At the visit, study staff would obtain informed consent in person.

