Prior to any analyses, endpoints data for each group will be closely inspected for the potential presence of unusual values; effort will be made to conserve all data. Analyses will be carried out in SAS 9.4 (SAS Institute, Cary NC) at the 5% significance level; point and 95% interval estimates will be obtained for relevant metabolic group comparisons. Parametric techniques will be first choice and nonparametric equivalents if assumptions are not met. Special attention will be paid to unequal variances.

The study planned four groups of children: lean, healthy obese/overweight, insulin-resistant obese/overweight, and overweight/obese with T2D. Primary comparison of interest are these three: the average of insulin-resistant and T2D obese children compared to (i) lean children and (ii) healthy obese children; and (iii) lean children compared to healthy obese children. Outcomes important to this aim are proportions of T_{reg} cells among circulating CD4 $^{+}$ T cells and CD4 $^{+}$ T glycoATP and mitoATP production. Initially, we will use a one-factor ANOVA to analyze these outcomes (possibly with suitable transformations). Comparisons of interest will then be made with 0.05 significance level *t*-tests conducted within the ANOVA framework.

The requested sample sizes will provide about 0.80 power for detecting differences in means of size 0.8 SD for comparisons (i) and (ii) and size 0.9 SD for comparison (iii), where SD is the within-group standard deviation (a.k.a., root mean square error from the ANOVA). For proportions of T_{reg} cells – a primary outcome of interest, an estimate of the SD is 2.3 percentage points (ref Table 1 of Arismendi et al.⁴²). So, if the means differ by at least 1.85 percentage points in comparisons (i) & (ii) and by 2.10 percentage points for comparison (iii), we will be able to detect these differences with a reasonably high probability (0.80 or higher).

Ethical Considerations

This study will be conducted in accordance with all applicable government regulations and University of Arkansas for Medical Sciences research policies and procedures. This protocol and any amendments will be submitted and approved by the UAMS Institutional Review Board (IRB) to conduct the study.

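### Primary comparisons (i) and (ii) may include children already on metformin at the first draw, and the plan has no drug-free analysis to show whether that matters

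*Combined protocol and SAP*

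**What the plan says.** **Who may be on drug.** Under Study Population, the second block of inclusion criteria covers overweight or obese children with T2D or insulin resistance who are "Prescribed metformin (either not yet taking or began taking within 3 weeks of enrollment". The matching exclusion is "Taking metformin prescribed as part of their clinical care for longer than 3 weeks at the time of enrollment", so shorter use does not exclude.

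**When blood is drawn.** Recruitment states: "At the visit, study staff would obtain informed consent in person". Enrollment and the first visit therefore largely coincide. Study Design and Procedures requires an overnight fast, "except for water and medications the day of the visit", and states no metformin washout. A failed blood draw may be re-attempted at a later visit.

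**Which visit feeds Aim 1.** Data Analysis does not say. Only children prescribed metformin have a second visit: "All other children, will be asked to complete only the first visit". The first visit is thus the only one common to all groups.

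**What is compared.** Data Analysis names three primary comparisons. Two of them are "the average of insulin-resistant and T2D obese children compared to (i) lean children and (ii) healthy obese children"; the third is lean against healthy obese. The stated model is a one-factor ANOVA followed by t-tests within it. No exposure term, drug-naive restriction or sensitivity analysis is given.

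**What the drug is expected to do.** Aim 1 expects fewer Tregs and a higher share of glycolytic ATP in obese children with raised inflammatory markers. The Aim 2 hypothesis begins "In obese T2D patients, metformin treatment will increase circulating" Tregs, and goes on to predict more AMPK activation and a higher share of OXPHOS-derived ATP.

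**The concern.** Possible metformin exposure is tied to group membership. It can occur in the T2D group, which carries half the weight on the disease side of (i) and (ii), and is not expected in the lean and healthy overweight/obese groups. The drug is the one that Aim 2 predicts will move the same outcomes in the opposite direction. A small or null result in two of the three primary comparisons could then reflect early drug effect, absence of a disease difference, or both, and the analysis as specified does not separate them.

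The exclusion criteria already remove other medicines because they can affect the outcomes. The pilot T2D samples in Preliminary Data (Figure 2 methods) came from "treatment-naive type 2 diabetic" children, although there were only two of them.

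This is separate from whether the Aim 2 'before' sample is truly pre-treatment. Settling that question would leave comparisons (i) and (ii) unchanged.

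**Working it through.** **Inputs from the documents.** Four groups of about 20 (lean; healthy overweight/obese; insulin-resistant; T2D), from Study Population and Data Analysis. Significance level 0.05, taken as two-sided because the plan also gives 95% intervals. Target differences 0.8 SD for (i) and (ii) and 0.9 SD for (iii). Treg SD 2.3 percentage points.

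**Inputs not in the documents (assumed).** *f*, the share of the T2D group on metformin at the first draw; *r*, the share of the disease difference that up to three weeks of drug has reversed in those children.

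**Step 1: reproduce the plan's power.** Noncentral t, 80 − 4 = 76 df.
- (i) and (ii): SE = √(1/20 + 0.25 × (1/20 + 1/20)) = √0.075 = 0.274 SD. At 0.8 SD, power is 0.82.
- (iii): SE = √(2/20) = 0.316 SD. At 0.9 SD, power is 0.80.
- In Treg points: 0.8 × 2.3 = 1.84 (plan: 1.85) and 0.9 × 2.3 = 2.07 (plan: 2.10).

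The plan's figures hold, on the premise that no drug effect sits in the T2D mean.

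**Step 2: exposure in the T2D group only.** T2D has weight 0.5 in the averaged group, so the expected contrast is 0.8 × (1 − 0.5 × *f* × *r*) SD.

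| *f* | *r* | Contrast (SD) | Treg points | Power |
|---|---|---|---|---|
| 0 | – | 0.80 | 1.84 | 0.82 |
| 25% | 10% | 0.79 | 1.82 | 0.81 |
| 50% | 10% | 0.78 | 1.79 | 0.80 |
| 25% | 25% | 0.775 | 1.78 | 0.80 |
| 50% | 25% | 0.75 | 1.72 | 0.77 |
| 50% | 50% | 0.70 | 1.61 | 0.71 |
| 100% | 50% | 0.60 | 1.38 | 0.58 |

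**Step 3: if insulin-resistant children are exposed too.** The second inclusion block admits insulin-resistant children on metformin, while the third recruitment group is labelled T2D only. The plan does not say in which group they are analysed. If both groups were exposed equally, the factor becomes 1 − *f* × *r*: at 50% and 25% the contrast is 0.8 × 0.875 = 0.70 SD, power 0.71.

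**Step 4: precision of a drug-free analysis.** With *m* drug-free T2D children and 20 in each other group, SE = √(1/20 + 0.25 × (1/20 + 1/*m*)) and df = 60 + *m* − 4.

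| *m* | SE (SD) | df | Power at 0.8 SD |
|---|---|---|---|
| 15 | 0.281 | 71 | 0.80 |
| 10 | 0.296 | 66 | 0.76 |
| 5 | 0.335 | 61 | 0.65 |

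Using 20 drug-free insulin-resistant children alone against lean, SE is 0.316 SD and power at 0.8 SD is 0.70 (76 df).

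**The case against.** **The direction is not established.** A reader might infer that metformin does pull these contrasts toward zero. The documents do not show that. It rests on the study's own untested hypotheses. The background says metformin's potential to induce Tregs is otherwise unstudied in obese individuals, and that a placebo-controlled trial in pre-diabetic adults found lower mTOR activity at two months but unchanged AMPK activity. Nothing is reported at three weeks or less, and the study itself waits six months for its metformin comparison. This stands, and the direction must be stated as conditional.

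**The large power losses need strong inputs.** Falls to 0.71 or 0.58 in the T2D-only scenarios require half the disease difference to be reversed within three weeks in half or all of the group. Mild inputs leave power at the plan's figure of about 0.80. This stands too.

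**A drug-free analysis does not buy back power.** With 50% exposed and 25% reversal, the full sample has power 0.77 and the drug-free analysis 0.76. With 75% and 50%, both have 0.65. With everyone exposed there is no drug-free T2D mean to estimate. Children not yet on drug may also differ in time since diagnosis or severity. So the drug-free result should not be the sole basis for disease claims.

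**The information is not lost.** One might read the plan as leaving the data uninterpretable. That goes too far: the ANOVA is described as an initial step, the insulin-resistant group can be contrasted separately, and the metformin start date is needed anyway for eligibility and for timing the second visit.

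**Absence of exposure elsewhere is inferred.** The first inclusion block does not bar short metformin use. It is simply not expected in lean and healthy overweight/obese children.

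What remains is that no analysis is prespecified to show whether early exposure matters.

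**Conclusion.** The point holds as a gap in the prespecified analysis. Eligibility allows up to about three weeks of metformin on the disease side of two primary comparisons, the first visit is the natural sampling point, and the stated model ignores exposure. Any early drug effect would be part of the estimated disease difference: toward zero if the study's hypotheses hold, possibly away from zero if there is no disease difference. Comparison (iii) should be little affected.

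The size cannot be derived from the documents. With a true 0.8 SD difference, 20 per group, exposure confined to T2D and the assumed ranges shown, power runs from essentially unchanged to 0.58. The documents do not support concluding that the comparisons are invalid or that bias is certain. This is a cheap improvement to the plan.

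**What to change.** In Data Analysis:

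1. State that Aim 1 uses first-visit samples, and in which group insulin-resistant children prescribed metformin are analysed.
2. Record for each child whether any metformin was taken before the first draw (including a re-attempted draw) and for how many days. The protocol already lets staff review medical and pharmacy records.
3. Prespecify that (i) and (ii) are reported for all children and again, as a sensitivity analysis, with T2D and insulin-resistant children limited to samples drawn before any metformin. Report the number of drug-free children per group.
4. Give a fallback. If too few T2D children are drug-free to estimate that group's mean, also report the contrast using metformin-naive insulin-resistant children alone, and describe the all-children estimate as a difference that includes possible early drug effect. Set the minimum number before the data are examined.

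**Cost.** One derived variable and one further model. The drug-free estimate is less precise, as shown in the working, and carries the selection risk noted above. No change to any child's treatment or its timing is needed.

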treatment in pre-diabetic adults reduced mTOR activity in PBMC despite increases at the gene expression level; however, AMPK activity was not changed by metformin. Metformin's potential to induce T_{regs} has otherwise not been studied in obese individuals. We will take advantage of the fact that this AMPK activator is commonly prescribed in pediatrics and compare the immune and metabolic phenotypes of CD4⁺ T in obese insulin resistant/T2D children before and after metformin treatment. As such, we will explore whether a potential mechanism of action of metformin is via direct modulation of CD4⁺T cell metabolism, induction of T_{regs}, and curbing inflammation.

The main purpose of this proposed study is to determine whether the immunometabolic phenotypes of CD4⁺T cells from obese children is skewed towards T_{eff} with mTOR-driven glycolysis and away from T_{regs} with AMPK-driven OXPHOS and whether metformin can reverse the immunometabolic phenotypes. These studies are imperative to begin testing and implementing strategies targeting the AMPK and mTOR pathways to combat obesity-associated inflammation and prevent progression into serious health complications. This translational research will move the field forward in several ways. First, we will gain insight into the pathophysiology of obesity-associated inflammation and the progression into insulin resistance and T2D. Second, we have the opportunity to uncover novel therapeutic avenues for obesity-associate inflammation and prevention of metabolic dysfunction that target immune cell metabolism. Third, we may identify an immunometabolic phenotype that correlates to risk for developing T2D and/or cardiovascular dysfunction and could be used to monitor treatment response in future treatment trials. The findings from this study will form the preliminary data for a planned R01 application to the NIDDK to be submitted in Year 2. The goal of that proposal will be to conduct additional translational studies to expand upon this study and begin testing the ability to modifying bioenergetic control pathways to combat obesity-associated inflammation.

Preliminary Data

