The formal consent of each subject, using the IRB-approved consent form, will be obtained before that subject is submitted to any study procedure. All participants for this study will be provided a consent form describing this study and providing sufficient information in language suitable for participants/parent/legally authorized guardian to make an informed decision about their participation in this study. The person obtaining consent will thoroughly explain each element of the document and outline the risks and benefits, alternate treatment(s), and requirements of the study. The consent process will take place in a quiet and private room, and participants/parent/legally authorized guardian may take as much time as needed to make a decision about their participation. Participation privacy will be maintained and questions regarding participation will be answered. No coercion or undue influence will be used in the consent process. This consent form will be signed by the parent or legally authorized guardian. Written assent will be obtained from participants aged 7-17 years, inclusive. A copy of the

Title: Immunometabolism in Pediatric Obesity

PI: [name].

signed consent will be given to the participants/parent/legally authorized guardian, and the informed consent process will be documented in each subject's research record. A signed copy of the consent form may be placed in patients' medical record. We request a waiver of consent for subjects who turn 18 while their samples are still available for use and who may still have data collected from their medical records, for the purposes of this study and/or for future research studies if consent obtained for this purpose. If the waiver is approved by the institutional review board and samples are still available for use/data is still being collected when a participant turns the age of 18, the participant will not be re-contacted to sign a consent form. However, these participants can contact study staff after they turn 18 to ask that any remaining samples be removed and data collection stop. In addition, participants may be re-contacted about participating in future research studies.

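### Aim 2's before-metformin sample can be drawn up to about 3 weeks into treatment, and the analysis plan makes no use of exposure at that draw

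*Combined protocol and SAP*

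**What the plan says.** Specific Aim 2 compares immune and metabolic phenotypes "between T2D children before and after metformin". The background gives the same contrast, "in obese insulin resistant/T2D children before and after metformin treatment", and presents it as exploratory.

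Study Population sets the exposure allowed at entry. Inclusion reads "Prescribed metformin (either not yet taking or began taking within 3 weeks of enrollment". The matching exclusion removes only children "Taking metformin prescribed as part of their clinical care for longer than 3 weeks at the time of enrollment".

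Three further statements fix what this means for the first blood sample:

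- Recruitment: "At the visit, study staff would obtain informed consent in person". Ethical Considerations adds that consent "will be obtained before that subject is submitted to any study procedure".
- Study Design and Procedures: the overnight fast applies "except for water and medications the day of the visit", so metformin is not withheld.
- Study Design and Procedures: after an unsuccessful procedure, the family "may be asked to return to the study site for an additional visit to re-attempt the procedure". No time limit is stated.

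The second visit is set at 6 months, plus or minus 2 weeks, counted from the start of metformin. The goal is 10 children completing it. The Data Analysis section describes a one-factor ANOVA with three between-group comparisons. It states no before/after analysis and no role for metformin status at the first draw.

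**The concern.** The eligibility rule and the aim do not match. The aim needs an untreated first sample, while the rule accepts one taken on treatment. A child who has already responded in part contributes only the rest of the response to the measured change. If metformin acts early in the hypothesised direction, the average change is pulled toward zero.

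With about 10 pairs there is little room for that. A small or null change could mean that metformin does little to these cells, or that part of the effect was already in the first sample. A report that does not say how many first draws were untreated leaves the reader unable to weigh the two. The background says that the findings will serve as preliminary data for a further grant application, so the interpretation matters even though the aim is exploratory.

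**Working it through.** **Can a first draw be on drug, and for how long?** The criteria allow 0 to 3 weeks of metformin at enrollment. Consent is taken in person at the visit and precedes any procedure. If enrollment means consent, a successful first draw falls at no more than about 3 weeks of treatment. Only a redraw can fall later. Against a 26-week interval, 3 weeks is 3/26 = 11.5% of the exposure time.

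**The plan's own figures.** No power or test is given for Aim 2. The stated power of about 0.80 belongs to the cross-sectional comparisons. It reproduces with 76 error degrees of freedom, at 0.82 for 0.8 SD in (i) and (ii) and 0.80 for 0.9 SD in (iii). It says nothing about the before/after change.

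**Illustration for Aim 2.** From the documents: 10 pairs, the 5% level, a window of 0 to 3 weeks, and about 26 weeks to the second visit. Assumed here: a two-sided paired t-test, a true change large enough for 0.80 power with untreated first draws, four onset patterns, and k of 10 first draws on drug.

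1. From the noncentral t with 9 degrees of freedom, power of 0.80 needs d = 0.996 SD of the paired change.
2. The share of the 26-week effect present at week w is w/26 if linear, or (1 − 2^(−w/h)) / (1 − 2^(−26/h)) for half-time h weeks.
3. The mean change becomes d × (1 − share × k/10). For example, with h = 4 and draws spread evenly over 0 to 3 weeks, the mean share is 0.223. With k = 5 the understatement is 0.223 × 0.5 = 11%, so d falls to 0.885 and power to 0.70.

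| Onset | Mean share, 0–3 weeks | k = 2: understated, power | k = 5: understated, power |
|---|---|---|---|
| Linear over 26 weeks | 0.058 | 1%, 0.79 | 3%, 0.78 |
| Half-time 8 weeks | 0.133 | 3%, 0.78 | 7%, 0.74 |
| Half-time 4 weeks | 0.223 | 4%, 0.76 | 11%, 0.70 |
| Half-time 2 weeks | 0.378 | 8%, 0.74 | 19%, 0.62 |

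A simulation that keeps the mix of affected and unaffected pairs gives slightly lower power for k = 5: 0.78, 0.74, 0.70 and 0.60.

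**How far it could go.** If all five on-drug draws fell at exactly 3 weeks, power would be 0.75, 0.69, 0.61 or 0.48 across the four patterns (0.75, 0.68, 0.59 or 0.43 in the simulation). The criteria also allow all 10 first draws to be on drug. With all 10 at 3 weeks and a 2-week half-time, the share is 0.647, d falls to 0.996 × 0.353 = 0.352, and power is 0.17. At the other end, no effect by 3 weeks means no loss.

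**What an untreated-only estimate could show.** With 5 untreated pairs at d = 0.996, power is 0.40. The 95% interval half-width is t(0.975, n − 1)/√n: 2.776/√5 = 1.24 SD for 5 pairs, against 2.262/√10 = 0.72 SD for 10.

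**The case against.** The window is deliberate and disclosed. It appears in both inclusion and exclusion, and the design section says openly that children may have been recently prescribed the drug. Metformin is started by clinical care, half the group is expected to decline the second visit, and only 10 pairs are sought. A strict untreated rule could cost pairs the study cannot spare. This stands, and it is why the window should stay.

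The harm depends on an unknown onset. The nearest evidence in the background is a placebo-controlled trial in pre-diabetic adults, where two months of metformin lowered mTOR activity in mixed blood cells but left AMPK activity unchanged. AMPK activation is one of Aim 2's hypothesised outcomes, so for that outcome the trial gives no support to a material effect by 3 weeks. The mTOR result points the other way. Neither result concerns CD4+ T cells in children or speaks to 3 weeks, so the onset stays open.

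No data are lost. The second visit is timed from the metformin start, so the start date has to be known, and the protocol allows medication questions and record review. Exposure at the first draw can be worked out later. That is correct, but the plan does not say it will be, and which first draws count as untreated is better fixed before results are seen.

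The absence of any written before/after analysis is a separate gap that would exist even if every first draw were untreated. On its own it is missing detail. The conflict between the entry rule and the aim is what makes this point distinct.

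**Conclusion.** The point holds in a limited form. As written, the plan can label as before-treatment a sample taken up to about 3 weeks into treatment, and its analysis text does not use that exposure. If metformin acts early in the hypothesised direction, the measured change is too small.

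The range of 3% to 19% understatement, with power of 0.78 to 0.62 from an assumed 0.80, rests on 5 of 10 first draws being on drug, an even spread over 0 to 3 weeks, the four onset patterns and a paired t-test. None of these comes from the documents.

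A reader might infer three stronger things. One is that the before/after comparison is invalid. The documents do not support this, because first draws may all be untreated and the effect may be absent at 3 weeks. The second is that the loss has a known ceiling. It does not, since the criteria put no cap on the share of children on drug. The third is that the window should be closed, but nothing in the documents shows that this would be worth the pairs it might cost. Aim 2 is exploratory and lies outside the three primary comparisons, so this is a change of low to moderate priority.

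**What to change.** Keep the 3-week window and all pairs, and make four additions:

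1. For children who have not started metformin, schedule the first draw before the first dose whenever this does not delay treatment.
2. Derive days on metformin at the first draw, or at the redraw if there is one, from the start date already needed to time the second visit.
3. In the Data Analysis section, describe the all-pairs result as the change from first draw (untreated or up to about 3 weeks treated) to 6 months, and report the number of untreated first draws. Note any redraw that falls later than 3 weeks.
4. Add a supportive estimate with a 95% interval, limited to pairs whose first draw was untreated.

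The cost is minor scheduling effort, which depends on clinicians' start dates, and a few sentences of analysis text. No child is excluded and no visit is added. The untreated-only estimate will be imprecise at the sizes shown above. It helps interpretation but cannot by itself settle a null result.
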